#### 4.10.2 Adverse Events

##### 4.10.2.1 Definition of Treatment-Emergent Adverse Event (TEAE)

TEAEs are defined as adverse events that occurred on or after the first administration of Study Drug or worsened relative to the pre-treatment state. Note that imputed dates will be used for defining TEAEs.

In addition, if severity of an AE changes during the study, a separate AE will be recorded for each severity on the AE CRF. The “first” and “second” AEs will be defined based on AE start date, and AE start date of the second record will be the same as AE stop date of the first record. AE severity (mild/moderate/severe) should be compared pairwise between these linked events when defining TEAEs. Consider 2 cases below:

Case 1: The first AE record in the pair occurs before first dosing, and the second AE record occurs after first dosing.

If the AE severity of the second record is worse than that of the first record, then only the second AE is deemed as a TEAE. Otherwise, neither record is considered as TEAE.

Case 2: Both AE records in the pair occur after first dosing.

The worst AE will be deemed as a TEAE.

All TEAEs identified based on the rules above will be summarized in the event number analysis.

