#### 4.10.2.5.6 Local Cutaneous Reactions at the Injection Site

Local cutaneous reaction at injection site (LCRIS) is defined as (A) moderate or severe AEs with the preferred terms (PTs) including Injection site erythema, Injection site swelling, Injection site pruritus, or Injection site pain that started on the day of injection, persisted for at least 2 days (i.e., event onset date on the day of injection and resolution date not on the day of injection or the day after injection) or ongoing; or (B) any AE at the Study Drug injection site, regardless of severity, that leads to discontinuation of study drug, where AE at the Study Drug injection site is the principal reason for discontinuation.

LCRIS will be summarized by PT for each treatment group and total olezarsen treated. Patients with moderate, severe and any LCRIS will also be summarized. Discontinuations due to AE at the injection site will be summarized separately.

Percentage of injections leading to LCRIS will be summarized by PT and overall using the descriptive statistics. Additionally, percentage of injections leading to LCRIS will be summarized by moderate, severe severity and discontinuation of Study Drug due to AE at injection site.

Percentage of injections leading to LCRIS will be calculated as follows for each subject:  $(A/B) \times 100$ , where A = number of injections with an LCRIS, and B = total number of injections. Doses that are split across multiple injections are counted as a single injection.

The duration to resolution of a LCRIS and the time to onset of the first event will be summarized descriptively by treatment group and total olezarsen treated. If there are multiple LCRIS related to an injection and no overlap between events, the duration will be calculated as the sum of the duration of all LCRIS that are related to the injection. If there are overlaps, the duration will be calculated using the earliest start date and latest stop date of all LCRIS that are related to the injection. For unresolved LCRIS with missing stop date, the last participation date will be used in the calculation.

In addition, for patients who experienced LCRIS, the number of injections prior to the first LCRIS will also be summarized descriptively by treatment group and total olezarsen treated.

The LCRIS events will be provided in a listing.

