#### 4.10.2.5.7 Injection Site Reaction

Injection site reaction (ISR) is defined as any AE with PT or verbatim term containing 'Injection Site' that persisted for at least 2 days or ongoing. ISR will be summarized by PT for each treatment group and total olezarsen treated.

Percentage of injections leading to ISRs will be summarized by PT and overall using the descriptive statistics.

Percentage of injections leading to ISR will be calculated as follows for each patient:  $(A/B) \times 100$ , where A = number of injections with an ISR, and B = total number of injections. Doses that are split across multiple injections are counted as a single injection.

The duration to resolution of an ISR and the time to onset of the first event will be summarized descriptively by treatment group and total olezarsen treated. If there are multiple ISRs related to an injection and no overlap between ISRs, the duration will be calculated as the sum of the duration of all ISRs that are related to the injection. If there are overlaps, the duration will be calculated using the earliest start date and latest stop date of all ISRs that are related to the

injection. For unresolved ISRs with missing stop date, the last participation date will be used in the calculation.

In addition, for patients who experienced ISR, the number of injections prior to the first ISR will also be summarized descriptively by treatment group and olezarsen treated.

ISR will be listed by preferred term.

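### Splitting adverse events by severity and keeping the worst record dates worsening TEAEs late, and the split itself makes the LCRIS definition miss multi-day moderate reactions

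*Combined protocol and SAP*

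**What the plan says.** SAP 4.10.2.1 opens with a general rule: "TEAEs are defined as adverse events that occurred on or after the first administration of Study Drug", or that worsened relative to the pre-treatment state. It then deals with events that change grade: "a separate AE will be recorded for each severity on the AE CRF", and "AE start date of the second record will be the same as AE stop date of the first record". Protocol 9.4.3.5 fits this, since a change in severity is one of the outcomes that can close a non-serious record.

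Two cases follow.

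- **Case 1** (first record before dosing, second after): if the second is worse, "then only the second AE is deemed as a TEAE"; otherwise neither counts.
- **Case 2** (both records after dosing): "The worst AE will be deemed as a TEAE".

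The section closes with the use of the result: "All TEAEs identified based on the rules above will be summarized in the event number analysis".

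Several later derivations depend on record dates:

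- LCRIS limb (A), SAP 4.10.2.5.6: moderate or severe events with listed injection-site terms "that started on the day of injection, persisted for at least 2 days" or ongoing. The SAP explains this as resolution later than the day after injection.
- Injection site reaction (ISR), SAP 4.10.2.5.7: any injection-site event "that persisted for at least 2 days or ongoing".
- Flu-like reactions, SAP 4.10.2.5.8: listed terms that begin on the injection day or the day after.
- SAP 4.10.2.5.3 and 4.10.2.5.4: a 7-day onset window in the algorithmic hypersensitivity query, and time to first AKI event, both stated on TEAEs.

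**The concern.** Once an event has been split, no single record carries both its true onset and its true resolution. Case 2 then keeps one of those records. The SAP never says to restore the dates of the whole event before an onset, window or persistence rule is applied.

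Two things are at stake. Onset summaries based on TEAEs can be systematically late for events that worsen. And LCRIS, the SAP's measure of moderate or severe local intolerance to an injected drug, can omit reactions that began on the injection day, lasted beyond the next day and reached moderate severity.

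**Working it through.** The documents state no figure on this point, so there is none to reproduce. The check applies the date rules literally.

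**Notation and inputs.** Day 0 is the injection day. An event starts on day o, changes severity on day c and resolves on day e. By SAP 4.10.2.1, record 1 runs from o to c and record 2 from c to e.

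**Step 1: the record Case 2 retains.**

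- Worsening: record 2 is kept. Onset is late by c − o days; the stop date is right.
- Improving: record 1 is kept. The stop date is early by e − c days; the onset is right.

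**Step 2: timing measures stated on TEAEs.** For a worsening event, time to first AKI TEAE is lengthened by c − o days. A hypersensitivity event that begins inside the 7-day window and worsens outside it fails the algorithmic query on its retained record. Improving events are not affected here.

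**Step 3: LCRIS limb (A), all records kept.** A record must be moderate or severe, start on day 0 and stop on day 2 or later.

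- Mild on day 0, moderate from day 1: the mild record fails on severity, the moderate record on start day.
- Moderate on day 0, mild from day 1: the moderate record stops on day 1 and fails on persistence; the mild record fails on severity and start day.

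Both reactions are lost with or without the TEAE filter.

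**Step 4: enumeration.** Set o = 0, c = 1 to 7 and e = c + 1 to 8. The number of (c, e) pairs is 7 + 6 + 5 + 4 + 3 + 2 + 1 = 28. There are three worsening severity pairs and three improving ones, so 3 × 28 = 84 patterns in each direction. Assumptions: the whole event is judged at its peak severity, and ISR persistence means stop minus start of at least 2 days. Every whole event then meets LCRIS, ISR and flu-like timing. Patterns missed, out of 84:

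| Measure | Worsening, worst record only | Worsening, all records | Improving, worst record only | Improving, all records |
|---|---|---|---|---|
| LCRIS (A) | 84 | 63 | 21 | 21 |
| ISR | 21 | 3 | 21 | 3 |
| Flu-like timing | 63 | 0 | 0 | 0 |

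The LCRIS counts can be checked by hand.

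- Worsening, all records: every mild-to-moderate and mild-to-severe pattern fails (28 + 28 = 56). Moderate-to-severe fails only when c = 1, which has 7 resolution days. 56 + 7 = 63.
- Improving: failure occurs only when c = 1, so 7 × 3 = 21.

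No pattern produced a false positive.

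**Step 5: individual courses.** Duration is stop − start + 1. The flu-like column of reasoning concerns timing only.

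| Course | Whole event | Worst record only | All records |
|---|---|---|---|
| Mild day 0, moderate day 1, resolved day 5 | Onset 0, 6 days | Onset 1, 5 days; LCRIS lost | LCRIS lost |
| Moderate day 0, mild day 1, resolved day 5 | Onset 0, 6 days | Onset 0, 2 days; LCRIS and ISR lost | LCRIS lost |
| Mild day 0, moderate day 2, resolved day 6 | Onset 0, 7 days | Onset 2, 5 days; LCRIS and flu-like timing lost | LCRIS lost |
| Mild day 0, moderate day 1, resolved day 2 | Onset 0, 3 days | Onset 1, 2 days; LCRIS and ISR lost | LCRIS and ISR lost |

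**The case against.** The case for leaving the text alone has real force.

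- LCRIS, ISR and flu-like reactions are written on adverse events, while the neighbouring sections say TEAE. The only use 4.10.2.1 names for its rule is the event count, where it stops one event being counted twice. Nothing says the filter comes first.
- Case 1 contains the word only; Case 2 does not. The general definition would admit both Case 2 records.
- The LCRIS losses in Step 3 come from the split and the LCRIS conditions, not from Case 2.
- The duration rules in 4.10.2.5.6 and 4.10.2.5.7 already sum or merge several records tied to one injection.
- Exposure-adjusted incidence is specified for the two adverse events of special interest (4.10.2.4) and MACE (4.11.3.1), not for these reactions.
- The worst record is always kept, so patient-level incidence by term and maximum severity (4.10.2.2) do not change, and all events are listed.
- Protocol 2.3.4 reports injection site reactions in Phase 2 at 12.2% versus 4.2%, mostly mild. A reaction that stays mild cannot meet LCRIS limb (A).

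Most of this stands, and it confines the point. It does not remove it. A Case 2 rule that left both records as TEAEs would have no purpose, so the natural reading drops one, and the AKI and hypersensitivity timing is stated on TEAEs. That the LCRIS loss comes from the split means it persists under either reading. The duration rules act only on records that already qualify as LCRIS or ISR, so a segment that failed the definition cannot be merged back.

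**Conclusion.** Two defects hold. First, for on-treatment events that worsen, onset in TEAE-based timing analyses is late by the interval between true onset and worsening. This rests on reading Case 2 as dropping the milder record. Second, LCRIS limb (A) misses some multi-day reactions that start on the injection day and reach moderate severity, whichever records are used: 63 of 84 worsening and 21 of 84 improving patterns. That count rests on judging the whole reaction at its peak severity. In the patterns examined the error is always under-counting.

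A reader might infer that every severity change misdates the event, that ISR, flu-like reactions, durations and exposure-adjusted rates are all misclassified, and that reactions on active drug are therefore under-reported. The documents do not support that:

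- Case 1 onset at worsening is appropriate.
- ISR has no start-day condition, and flu-like reactions have no persistence condition.
- With all records kept, flu-like timing loses nothing and ISR loses 3 of 84 patterns in each direction. The larger losses need a TEAE filter that the SAP does not state for these definitions.
- There is no rate of severity change, overall or by arm, so neither the number of patients affected nor any difference between arms can be computed.

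The consequence is limited to descriptive safety summaries. It is still worth correcting, because following the text as written drops real reactions, and two programmers could build different ISR, flu-like and duration tables.

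**What to change.** In SAP 4.10.2.1, state that the Case 2 worst-record rule applies to event counts and severity tables only. Add that LCRIS, ISR, flu-like reactions, their durations, and TEAE-based time-to-onset or onset-window analyses use linked on-treatment records collapsed into one episode: the earliest on-treatment start, the latest stop and the maximum severity. Leave Case 1 unchanged. Under this rule all four courses in Step 5 meet LCRIS, ISR and flu-like timing, with onset on day 0 and durations of 6, 6, 7 and 3 days.

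The cost is one clarifying paragraph and a short derivation step; severity tables do not change. The change does settle a question of definition: a reaction that is mild on the injection day and moderate later would count as LCRIS, so LCRIS counts may rise slightly. The SAP should say that this is intended.

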##### 4.10.2.2 Analysis for TEAEs

All AEs will be coded to SOC and PT using the MedDRA. The final MedDRA version used will be designated in the clinical study report. The frequency and incidence of AEs will be summarized by SOC and PT. The SOC's will be presented in alphabetical order, and the PTs will be presented in descending frequency order within each SOC. Subjects reporting more than one AEs will be counted only once for each level of summation (most severe incident for the severity tables and most related incidence for the relationship tables).

The frequency of patients with any incidences of AEs and the number of events will be presented by treatment group and total olezarsen treated for the following summaries:

- Any TEAEs by SOC and PT
- Any TEAEs by PT
- TEAEs related to Study Drug by SOC and PT. Related is defined as “Related”, “Possible”, or missing relationship to Study Drug

- Any TEAEs by maximum severity, SOC and PT. At each severity level of subject summarization, a subject is classified according to the highest reported severity if the subject reported one or more events. TEAEs with missing severity will be categorized as "Missing" for this summary.
- TEAEs related to Study Drug by severity, SOC, and PT
- Serious TEAEs by SOC and PT
- Serious TEAEs related to Study Drug by SOC and PT
- Serious TEAEs related to Study Drug by SOC and PT
- Serious TEAEs by severity
- Serious TEAEs related to study drug by severity
- TEAEs leading to permanent Study Drug discontinuation by SOC and PT
- TEAEs related to Study Drug leading to permanent Study Drug discontinuation by SOC and PT
- TEAEs leading to death by SOC and PT
- TEAE with an incidence rate > 5% in any treatment group by PT
- Non-serious TEAE with an incidence rate > 5% in any treatment group by PT

An overall summary of frequency and incidence of AEs of above unique categories will be provided by treatment group and total olezarsen treated. By-subject listing of all AEs will be provided, in which non-treatment emergent AEs will be included and be noted. The following additional listings will be provided for TEAEs unless otherwise specified.

- Listing of treatment-emergent SAEs
- Listing of TEAEs related to study drug
- Listing of TEAEs leading to discontinuation of Study Drug
- Listing of all deaths

To define TEAEs, the algorithm in Section 4.10.2.3 will be applied to impute missing or partial start date or end date. Original reported dates will be used for listings.

#### 4.10.2.3 Missing Date for Adverse Events

For AEs, the following imputation rules will be applied to impute missing dates under conservative principles. The imputed dates will be used for defining TEAEs.

##### **For start dates:**

- If year, month and day are all missing, then assign the date of first dose of Study Drug.
- If month and day are missing and year is:
  - the same as the year of the first dose of Study Drug, then assign the month-day of first Study Drug
  - earlier than the year of the first dose of Study Drug, then assign December 31
  - after the year of the first dose of Study Drug, then assign January 1
- If only day is missing, and month-year is:
  - the same as the month-year of the first dose of Study Drug, then assign the day of first Study Drug
  - earlier than the month-year of the first dose of Study Drug, then assign the last day of the month.
- after the month-year of the first dose of Study Drug, then assign the first day of the month.

**For end dates:**

Imputation will be performed for the end date only if the day or month is missing (i.e., year is present) for a resolved AE as follows:

- If month and day are missing and year is:
  - the same as the year of the last dose of Study Drug, then assign the month-day of the last dose of Study Drug
  - otherwise, assign December 31
- If only day is missing, then assign the last day of the month.

If the imputed start date is later than the imputed end date, then set the imputed start date to the imputed end date.

*4.10.2.4 Adverse Events of Special Interest*

The following AEs are considered AE of special interest for the study. These events will be reviewed and evaluated to determine if they meet the criteria.

- Platelet count < 50,000/mm^3 accompanied by a major bleeding (MB) event or clinically relevant non-major bleeding (CRNMB) event, or platelet count of < 25,000/mm^3 irrespective of a MB or CRNMB event.
- Use of medications (prophylactic treatment such as antihistamines, acetaminophen, non-steroidal anti-inflammatory drugs [NSAIDs], corticosteroids, etc.) as pre-treatment to avoid a hypersensitivity reaction or recurrence of a previous hypersensitivity reaction.

Those events will be individually reviewed and evaluated to determine if they meet the criteria.

The following analyses will be provided.

- The number and percentage of patients experiencing events as well as the total number of reported events, risk difference and its 95% CI in the crude incidence rates between each active treatment group (or total olezarsen treated) and pooled placebo group, classified by PT, will be tabulated by treatment group and total olezarsen treated.
- A cumulative incidence plot if data supported.
- EAIR, risk difference and its 95% CI in EAIRs between each active treatment group (or total olezarsen treated) and pooled placebo group, and EAER. classified by PT, will be tabulated by treatment group and total olezarsen treated.

*4.10.2.5 Other Adverse Events of Interest*

The number and percentage of patients experiencing events as well as the number of reported events, risk difference and its 95% CI in the crude incidence rates between each active treatment group (or total olezarsen treated) and pooled placebo group, classified by PT (unless otherwise specified), will be tabulated by treatment group for the following AEs of Interest.

*4.10.2.5.1 Bleeding TEAEs*

Bleeding TEAEs will be analyzed by SOC and PT for the following categories.

- Bleeding TEAEs (defined based on the 'Haemorrhages' Standardized MedDRA Query [SMQ, both narrow and broad scope])
- Clinical bleeding TEAEs, i.e. bleeding TEAEs excluding events at the injection site and events related to a laboratory value

- Clinical bleeding events with concomitant anticoagulant or antiplatelet medication
- Clinical bleeding events without concomitant anticoagulant or antiplatelet medication

#### 4.10.2.5.2 Thrombocytopenia TEAE

Thrombocytopenia TEAE will be analyzed as follows:

- Thrombocytopenia TEAE (defined based on the 'Thrombocytopenias' High Level Terms [HLT] or 'Platelet count decreased' PT)

#### 4.10.2.5.3 Hypersensitivity TEAE

Hypersensitivity TEAEs will be analyzed for the following categories.

- Hypersensitivity TEAE (defined based on the Hypersensitivity SMQ [narrow scope only]) by SOC and PT
- TEAEs in the Hypersensitivity FMQ (narrow) by PT.
- Serious TEAEs, fatal TEAEs and TEAEs leading to treatment discontinuation in the Hypersensitivity FMQ (narrow) by PT
- Action taken with drug due to TEAEs in the Hypersensitivity FMQ (narrow)
- Rescue medication used in management TEAEs in the Hypersensitivity FMQ (narrow)
- TEAEs in the Hypersensitivity FMQ (broad search, incorporates broad and narrow FMQ preferred terms to maximize sensitivity) by PT.
- Serious TEAEs, fatal TEAEs and TEAEs leading to treatment discontinuation in Hypersensitivity FMQ (broad search, incorporates broad and narrow FMQ preferred terms to maximize sensitivity) by PT
- Action taken with drug due to TEAEs in the Hypersensitivity FMQ (broad search, incorporates broad and narrow FMQ preferred terms to maximize sensitivity)
- Rescue medication used in management TEAEs in Hypersensitivity FMQ (broad search, incorporates broad and narrow FMQ preferred terms to maximize sensitivity)
- TEAEs in the Hypersensitivity algorithmic FMQ. The FMQ definition is using an algorithmic component of the PTs identified within the Hypersensitivity FMQ based on the locations that hypersensitivity is known to commonly affect, i.e., airway, skin, soft tissue, and systemic. In addition, the onset of event(s) is within 7 days of the treatment.
- TEAEs in the Anaphylactic reaction FMQ (narrow) by PT
- Serious TEAEs, fatal TEAEs and TEAEs leading to treatment discontinuation in Anaphylactic reaction FMQ (narrow) by PT

For patients who had hypersensitivity reactions, either in FMQ narrow, broad, or algorithmic, the time to onset of the first event will be summarized using descriptive statistics.

For patients who had serious hypersensitivity reactions or discontinued study drug due to hypersensitivity reactions, either in FMQ narrow, broad, or algorithmic, a graphical patient profile including selected laboratory tests will be provided.

#### 4.10.2.5.4 Renal Impairment TEAE

Renal impairment TEAEs will be analyzed for the following categories.

- Renal impairment TEAEs (defined based on the 'Acute renal failure' SMQ (narrow and broad)) by SOC and PT
- TEAEs, serious TEAEs, fatal TEAEs, and TEAEs leading to treatment discontinuation in the AKI FMQ (narrow) by PT
- TEAEs, serious TEAEs, fatal TEAEs, and TEAEs leading to treatment discontinuation in the AKI FMQ (broad) by PT
- Patients who met the original criteria and revised criteria in the renal monitoring and stopping criteria and patients who discontinued study treatment or post treatment follow-up due to TEAEs in Acute Kidney Injury (AKI) FMQ (narrow or broad)
- For patients having treatment emergent proteinuria (defined as all events fall under proteinuria" SMQ (narrow and broad), the time to onset of the first event will be summarized using descriptive statistics
- For patients having treatment emergent albuminuria (defined as all related events fall under proteinuria SMQ narrow, including diagnosis tests for albumin/creatinine ratio), the time to onset of the first event will be summarized using descriptive statistics
- For patients who had AKI TEAE (FMQ narrow or broad), the time to onset of the first event will be summarized using descriptive statistics.
- For patients who had serious AKI TEAE (FMQ narrow or broad), or discontinued study drug due to AKI TEAE (FMQ narrow or broad), a graphical patient profile including but not limited to eGFR (by CKD-EPI formula 2021), serum creatinine, UACR, UPCR and selected electrolytes will be provided.
- For patients who had serious AKI TEAE (FMQ narrow or broad), or discontinued study drug due to AKI TEAE (FMQ narrow or broad) or protocol defined renal monitoring or stopping criteria (original or revised), a data listing including eGFR (by CKD-EPI formula 2021), serum creatinine, UACR and UPCR will be provided.

